11.5 Physical Examinations

Subject listings of all physical examination results by body system will be provided. Any changes from baseline will be recorded as adverse events.

12 RESOURCE UTILIZATION ANALYSES

Descriptive statistics of the following resource utilization parameters will be provided by treatment group:

- Number of hospitalizations for the ABSSSI from the first dose of study drug through the FU Visit.
- For those subjects who had at least one hospitalization, the number of days in the hospital from date of admission for the ABSSSI until discharge.

13 OTHER RELEVANT DATA ANALYSES/SUMMARIES

13.1 Protocol Deviations

A listing of all protocol deviations will be provided. Deviations will also be reviewed by the sponsor and categorized into general categories such as: randomization, at least one inclusion criterion not met, at least one exclusion criteria met, study procedures/visits not done, study visit outside window, use of prohibited medications or treatments, consent-IRB compliance issues, etc. The sponsor will also categorize the protocol deviations as major and minor. Review of protocol deviations will be conducted and finalized prior to unblinding the database. The number of subjects with at least one protocol deviation, the number of subjects with a minor protocol deviation, the number of subjects with a major protocol deviation, and the number of subjects with at least one major protocol deviation in each category will be presented by treatment group for the ITT population. A major deviation is defined as one that potentially affects the efficacy and/or safety analyses.

13.2 Prior and Concomitant Medications

All medications taken within 7 days prior to the date of informed consent through the Final Follow-up Visit will be recorded on the e-CRF. Prior medications will be summarized by WHODRUG (Version 01-Dec-2014) Anatomical Therapeutic Chemical Classification (ATC) level 3 (third level indicates the therapeutic/pharmacologic subgroup) and generic medication name. Medications are considered prior if taken prior to the first dose of test article or if their start date is unknown. Subjects will be counted only once for an ATC class and generic medication name. Concomitant medications taken during and after the study treatment period will be similarly summarized. Medications are considered concomitant if taken on or after the first dose of test article, or if their stop date is unknown or marked as continuing.

The proportion of subjects who receive the following prior and concomitant medications will be summarized by treatment group:

- Systemic and topical antibacterial medications taken within 7 days prior to first dose of test article and the reasons for receipt (mITT and CE-PTE populations)
- Systemic single dose, short-acting, non-oxazolidinone antibacterial taken within 72 hours prior to randomization
- Systemic and topical antibacterial medications (excluding test article) taken between first dose of test article and the EOT Visit (CE-EOT population) and the reasons for receipt (mITT and CE-EOT populations)
- Systemic and topical antibacterial medications (excluding test article) taken between first dose of test article and the PTE Visit (CE-PTE population) and the reasons for receipt (mITT and CE-PTE populations)
- Non-antibacterial medications taken 7 days prior to informed consent through the first dose of test article (mITT and Safety populations)

- Non-antibacterial medications taken from the first dose of test article through the Final Follow-up Visit (mITT and Safety populations)

15 APPENDICES

Appendix 1 Schedule of Events

Study Phase	Screening ^a	Double-Blind Treatment Phase						Follow-up Phase	
		Day 1	Day 2	Day 3 (ECR 48- 72 hr after first dose)	Day 7	Day 10 ^c	EOT ^d	PTE ^e	Final Follow-up ^f Day 30-37
Signed Informed Consent ^g	X								
Demographics	X								
Medical/surgical history and current medical conditions	X								
Prior and concomitant medications ^h	X	X-----X							
Clinical assessment of the site of infection ⁱ	X		X	X	X	X	X	X	X
Assessment of lesion size ^j	X		X	X	X	X	X	X	X
Diagnosis of ABSSSI and photograph of the lesion site ^k	X								
Numerical Rating Scale for pain at the primary lesion site	X			X			X	X	
SF-36v2 [®] Health Survey	X							X	
Physical examination ^l	X						X	X	
Vital signs									
Respiratory rate	X	X	X	X	X	X	X	X	X
Body temperature	X	X	X	X	X	X	X	X	X
Blood pressure	X	X ^m	X ⁿ	X ⁿ	X	X	X	X	X
Pulse/heart rate	X	X ^m	X ⁿ	X ⁿ	X	X	X	X	X
12-lead ECG ^o	X						X		
Urine dipstick test ^p	X								
Urine pregnancy test ^q	X								
Serum pregnancy test ^r	X						X	X	
Hematology ^s	X ^t			X	X	X	X	X	X
Serum chemistry ^s	X ^t			X	X	X	X	X	X
Blood culture ^u	X	As Clinically Indicated						X ^v	X ^v
Culture of infection site & Gram stain	X	As Clinically Indicated						X ^v	X ^v
Adverse Events ^w	X	X-----X							

Study Phase	Screening ^a	Double-Blind Treatment Phase						Follow-up Phase	
		Day 1	Day 2	Day 3 (ECR 48- 72 hr after first dose)	Day 7	Day 10 ^c	EOT ^d	PTE ^e	Final Follow-up ^f Day 30-37
Review of Inclusion and Exclusion Criteria/Randomization (if Eligible)	X								
Test Article Administration and Accountability ^x		X ^y	X ^z	X ^{aa}	X	X			
Plasma samples (in heparin) for PK analyses ^{bb}			X	X					
Assessment of need to continue therapy ^{cc}					X	X			
Investigator's Assessment of Clinical Response							X	X	

ABSSSI = Acute Bacterial Skin and Skin Structure infection; AE = adverse event; β-hCG = beta – human Chorionic Gonadotropin; ECG = electrocardiogram; ECR = Early Clinical Response; eCRF = electronic case report form; EOT = end of treatment; ICF = informed consent form; PK = pharmacokinetics; PTE = post therapy evaluation; SAE = serious adverse event.

- ^a Following the signing of an ICF, all Screening evaluations, with the exception of the blood culture sample collection, should be completed within the 24 hours prior to randomization. The blood culture sample collection should be completed within 24 hours prior to the first dose of test article.
- ^b Day 1 is the first day of test article administration. Subsequent study days are consecutive calendar days.
- ^c A Day 10 visit should be conducted for subjects with treatment extending beyond 9 days, unless this visit coincides with the EOT visit.
- ^d To be conducted on the calendar day of, or within 2 days following the last dose of test article. Should also be conducted for any subject who withdraws prematurely or terminates participation in the study before completion.
- ^e To be conducted 7 to 14 days after the subject's last day of study therapy.
- ^f To be conducted 30 to 37 days after the first dose of test article. The Final Follow-up assessment may be conducted via telephone contact or by another interactive technology for subjects who were considered to be Clinical Successes and had no AEs or clinically significant laboratory or ECG abnormalities noted at or after the PTE visit. Otherwise, the visit must be conducted in person.
- ^g Written and signed ICF must be obtained before any assessment is performed.
- ^h Treatments that have been administered within the 7 days prior to the date of signing the ICF or during the Screening phase will be recorded in the eCRF. All medications and significant non-drug therapies (including physical therapy and blood transfusions) administered after the first dose of test article must be recorded in the eCRF.
- ⁱ Semi-quantitative description of infection features. Must be assessed within 48 to 72 hours after the first dose.
- ^j Measurement of the subject's lesion by ruler length × width. The Screening measurement must be collected within 4 hours prior to randomization. A lesion measurement must be completed within 48 to 72 hours after the first dose.
- ^k Diagnosis of the type of ABSSSI (wound infection, cellulitis/erysipelas or major abscess) and anatomical location. A digital photograph of the infection site will be taken at Screening only.
- ^l A full physical examination will be completed at Screening; thereafter only changes from Screening measurements should be recorded as AEs in the eCRFs.
- ^m Blood pressure and pulse rate should be measured within 30 min before, and approximately (± 15 minutes) 1 hour after and 3 hours after the completion of the first dose on Day 1.

- ⁿ Blood pressure and pulse rate should be measured within 30 min before, and approximately (\pm 15 minutes) 1 hour after and 3 hours after the completion of the odd numbered doses on Days 2 and 3. In the event that the subject takes the dose before arriving for the office visit, the site should collect the 1 and 3 hour post dose measurements if possible, if not then a single measurement should be made at any time during the visit and the date and time recorded.
- ^o A 12-lead ECG should be performed at screening, at the EOT visit, and as otherwise clinically indicated.
- ^p A urine dipstick test will be performed locally at Screening.
- ^q All women will have a local urine pregnancy test at Screening.
- ^r All women will have blood collected for a serum β -hCG pregnancy test at the Central Laboratory at the Screening, EOT and PTE visits.
- ^s Blood will be collected for hematology (includes coagulation) and serum chemistry testing at the Central Laboratory at Screening and at the Day 3, Day 7, Day 10, EOT and PTE visits.
- ^t At the Screening visit, blood will be collected for local laboratory hematology and serum chemistry evaluations required for assessing subject eligibility.
- ^u If bacteria are isolated from blood cultures, repeat blood cultures should be collected. If subsequent blood cultures are also positive, repeat the blood cultures as necessary until negative blood cultures are obtained.
- ^v At the EOT and/or PTE visit, blood cultures and infection site specimen cultures and Gram stains should be obtained only for subjects who are clinical failures and require alternative antibacterial treatment for the infection under study.
- ^w A subject's AEs and SAEs will be recorded and reported from signing of the ICF to the Final Follow-up assessment.
- ^x A 6 hour fast is required before and a 2 hour fast is required following all odd numbered doses. The total duration of test article therapy for all subjects will be 7 to 14 days. Test article may be dispensed and reconciled by blinded personnel. Subjects will be asked to return all unused test article and packaging at each visit. At the EOT visit subjects will return the test article packaging and site staff will perform accountability.
- ^y Subjects should receive their first dose of test article at the site within 4 hours after randomization.
- ^z Subjects should be instructed not to take the odd numbered dose on Day 2 until they return to the site for the Day 2 visit.
- ^{aa} Subjects should be instructed not to take the odd numbered dose on Day 3 until they return to the site for the Day 3 visit.
- ^{bb} At selected sites, subjects who have agreed to participate in PK evaluation and have signed a separate PK evaluation consent form will have up to 4 blood samples collected between Days 2 and 3. The PK sample collection schedule for the individual subject will be provided by the Sponsor.
- ^{cc} At the investigator's discretion, all therapy may be discontinued after the 7th day of treatment, when the infection is considered clinically cured (based on normalization of the clinical signs and symptoms of infection and the investigator's clinical assessment that continued systemic antibacterial therapy is no longer needed).

Appendix 2 Summary of Efficacy Analyses

	48-72 Hours Post First Dose	End of Treatment Visit (EOT)	Post Therapy Evaluation Visit (PTE)
ITT	ECR		
mITT	ECR (primary efficacy)	IA	IA
Micro-mITT	ECR	Micro (by subject)	IA (by pathogen)
	ECR (by pathogen)	Micro (by pathogen)	IA (by pathogen and MIC)
	ECR (by pathogen and MIC)		Micro (by subject) Micro (by pathogen)
CE-EOT		IA	
CE-PTE			IA
ME-EOT		Micro (by subject)	
		Micro (by pathogen)	
ME-PTE			IA
			IA (by pathogen)
			IA (by pathogen and MIC)
			Micro (by subject) Micro (by pathogen)

ECR = Early Clinical Response; IA = Investigator Assessment of Response.

Appendix 3 Adverse Event and Prior/Concomitant Medication Date Imputations

Adverse Event Start/Stop Date Imputation

Imputation Rules for Partial Dates (D = day, M = month, Y = year)

Parameter	Missing	Additional Conditions	Imputation
Start date for AEs	D	M and Y same as M and Y of first dose of test article	Date of first dose of test article
		M and/or Y not same as date of first dose of test article	First day of month
	D and M	Y same as Y of first dose of test article	Date of first dose of test article
		Y prior to Y of first dose of test article but same as Y of screening date	Date of screening date
	D, M, Y	None - date completely missing	Date of first dose of test article
Stop date for AEs	D	M and Y same as M and Y of last dose of test article	Date of last dose of test article
		M and/or Y not same as date of last dose of test article	Use last day of month
	D and M	Y same as Y of last dose of test article	Date of last dose of test article
		Y not same as Y of last dose of test article	Use Dec 31
	D, M, Y	None - date completely missing	No imputation, but assume ongoing

Note: In all cases, if an estimated start date is after a complete stop date, use the first day of the stop date month. Similarly, if the estimated stop date is before a complete or imputed start date, use the last day of the start day month. In all cases, if it cannot be determined if the adverse event occurred prior to or after the first dose of test article, the adverse event should be defined as treatment emergent.

Prior and Concomitant Medication Start Date Imputation

Parameter	Type of Medication	Imputation
Start date for con meds	Non-Antibacterial	If it cannot be determined whether or not the start date of a medication (non-antibacterial) is prior to the first dose of test article, it will be assumed that the medication was received prior to the first dose of test article
	Antibacterial	Missing start dates for antibacterials will be queried for a value. If it cannot be determined whether or not the start date of an antibacterial is prior to the first dose of test article, it will be assumed that the medication was received prior to the first dose of test article unless the indication notes that the medication was received after the first dose of test article.
Stop date for con meds	Non-Antibacterial	If it cannot be determined whether or not the stop date of a medication (non-antibacterial) is after the first dose of test article, it will be assumed that the medication was received after the first dose of test article
	Antibacterial	Missing stop dates for antibacterials will be queried for a value. If it cannot be determined whether or not the stop date of an antibacterial is after the first dose of test article, it will be assumed that the medication was received after the first dose of test article unless the indication notes that the medication was received prior to the first dose of test article. If it cannot be determined whether the antibacterial was received prior to the assessment of Early Clinical Reponse, the EOT and/or the PTE Visit, the antibacterial will be assumed to have been received through the PTE Visit.

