8.3 Handling of Missing Data

Missing data will be handled as outlined below:

- All missing and partial dates for adverse events or for medications received after randomization will be queried for a value. If no value can be obtained, substitutions will be made as detailed in [Appendix 3](#). These substitutions will be used in calculations; however, the actual value recorded on the eCRF will be used in all listings.
- Missing start and stop times for prior and concomitant antibiotics will be queried for a value. If no value can be obtained but the site indicates the antibiotic was received (onset time) prior to the first dose of test article, 00:01 will be used for the onset time. If the site also indicates that the end time was prior to the first dose of test article, 00:01 will be used for end time. The actual value (blank) will be recorded on the eCRF and will be used in the listings.
- Missing times for lesion measurements will be queried for a value. If minutes are not available, the time will be recorded to the closest hour.
- If the time of the outpatient dose of test article on Day 1 is missing, it will be imputed to 23:59.
- If no value can be obtained for all other times for events and assessments occurring after randomization, the time will not be imputed but will remain missing.
- The severity and causality assessment for adverse events cannot be missing. Missing data will be queried for a value.

For clinical and microbiological response, missing data will be handled as follows:

- For the primary outcome measure (Early Clinical Response at 48 to 72 hours):
 - The subject will be considered to have missing data if there is no lesion size measurement (either length or width) at either baseline or 46 to 72 hours after the first dose of test article. Subjects with missing data will be defined as an Indeterminate response which is essentially a Clinical Failure for the primary analysis (mITT and ITT populations).
 - If the time of administration of the first dose of test article is missing, the subject will be defined as an Indeterminate response which is essentially a Clinical Failure for the primary analysis (mITT and ITT populations).
- For the secondary outcome measures (investigator's assessment of Clinical Response at the EOT and PTE Visits):

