TEAEs occurring (ie, with a start date and time) during the time period subjects are on treatment will be summarized by system organ class and preferred term.

In addition, all AEs (including non-TEAEs), serious TEAEs, and TEAEs leading to discontinuation of test article will be provided in listings by treatment group, study site, subject, verbatim term, MedDRA system organ class and preferred term, start and end date, seriousness

flag, severity, relationship to test article, relationship to study protocol, action taken with test article, non-test article action taken and outcome.

For subjects with a TEAE of nausea (based on the MedDRA preferred term), the total number of nausea events, descriptive statistics of the study day of onset of all nausea events, and descriptive statistics for the duration (in days) of all nausea events, will be presented by treatment group.

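### Imputed adverse-event stop dates have no upper limit, so a partial date can end a nausea event up to a year after Final Follow-up

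*SAP*

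**What the plan says.** SAP Appendix 3 treats partial adverse-event stop dates as follows.

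- Day missing, "M and Y same as M and Y of last dose of test article": the stop becomes the last-dose date.
- Day missing, "M and/or Y not same as date of last dose of test article": "Use last day of month".
- Day and month missing, year equal to the last-dose year: "Date of last dose of test article".
- Day and month missing, "Y not same as Y of last dose of test article": 31 December of the recorded year.
- Date wholly missing: no imputation; the event is taken as ongoing.

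The note under the table deals with a stop that would fall before the start. It says nothing about a stop that falls too late.

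SAP 8.3 has partial dates queried first. Of the values imputed when a query fails, it says: "These substitutions will be used in calculations; however, the actual value recorded on the eCRF will be used in all listings". SAP 8.1 defines a duration as end minus start plus one. SAP 11.1 plans, by treatment group, "descriptive statistics for the duration (in days) of all nausea events". Under SAP Appendix 1 (note w), adverse events are "recorded and reported from signing of the ICF to the Final Follow-up assessment", which is 30 to 37 days after the first dose.

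**The concern.** Two of the rules pick the latest day compatible with the partial date, and nothing ties that day to the time the subject was under observation. The study follows each subject for little more than a month, so a rule that can return 31 December of the following year can produce a duration that no data support.

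The output at stake is narrow. Treatment-emergent and on-treatment status in SAP 11.1 depend on start dates, and the listings show the recorded values. Nausea duration is the planned numerical summary that uses stop dates. Nausea is, however, a known effect of the oral drug (Protocol 9.1), and quantitative summaries report mean, standard deviation and maximum (SAP 8.1). Those are the statistics that a single extreme record distorts.

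**Working it through.** The documents state no figure for this point, so there is none to reproduce. The Appendix 3 rules, including the note, were applied literally to calendar dates. Inputs: treatment of 7 to 14 days (Protocol 14.3.1), Final Follow-up 30 to 37 days after first dose (SAP 8.6), duration = end − start + 1 (SAP 8.1). Calendar dates are illustrative.

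1. **Year rule, distance past Final Follow-up.** Take a last dose in one year and Final Follow-up in the next. The earliest such Final Follow-up is 1 January, which leaves 364 days to 31 December. The latest is 31 January (first dose 25 December, 7-day course, last dose 31 December, follow-up at 37 days), which leaves 365 − 31 = 334 days. If the stop year is a leap year, add one day. The range is 334 to 365 days.

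2. **Year rule, one event.** Onset 26 December, stop recorded only as the next year: 6 days in December + 365 = 371 days. Suppose the first dose was 20 December and the course lasted 10 days. Final Follow-up is then 19 to 26 January, and a stop capped there gives 6 + 19 = 25 to 6 + 26 = 32 days.

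3. **Month rule.**
   - First dose 21 June, last dose 30 June, Final Follow-up 21 to 28 July. A stop of 'July' becomes 31 July, 3 to 10 days after Final Follow-up. Onset 28 June gives 34 days.
   - First dose 24 May, last dose 2 June, Final Follow-up 23 to 30 June. A stop of 'July' becomes 31 July, 31 to 38 days after Final Follow-up. Onset 1 June gives 61 days. Here the whole recorded month lies after Final Follow-up, which the fix has to allow for.

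4. **Reach of the year rule.** For a stop within the recording period, the last dose must fall before New Year and Final Follow-up after it. With a course of T days and follow-up at F days, the number of first-dose dates is F − (T − 1). The minimum is 30 − 13 = 17 and the maximum 37 − 6 = 31. As a share of 365 these are 4.7% and 8.5%, so about 5% to 8%. This is a share of subjects only if accrual is even over the planned 12 months.

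5. **How many events could qualify.** With 704/2 = 352 subjects per arm, the nausea rates on the drug in Protocol 9.1 (10% in Phase 2, 27% in the terminated Phase 3 study) give about 35 to 95 events, counting one per affected subject. A mean duration of 2.5 days (assumed) crosses about 1.5 midnights, so 95 × 1.5/365 = 0.4 and 35 × 1.5/365 = 0.1 events per arm would span New Year. Not all of these also have the last dose before New Year. Post-treatment nausea starting after New Year could add a few. The site must then know the year but not the month, and the query must fail.

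6. **Effect of one such record on an arm's mean** (others at 2.5 days):
   - 95 events: (2.5 × 94 + 371)/95 = 606/95 = 6.4 days. Capped at 32 days: 267/95 = 2.8 days.
   - 35 events: (2.5 × 34 + 371)/35 = 456/35 = 13.0 days. Capped at 32 days: 117/35 = 3.3 days.

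   The median shifts by at most one place in the ordered durations.

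**The case against.** The strongest reply is that this will almost never happen. Partial dates are queried, all queries must be resolved before database lock (Protocol 25.3), and step 5 gives well under one candidate event per arm before the missing-month condition is applied. A 371-day maximum would be noticed, the recorded dates appear in the listings, the same rules apply to both arms, and the table carries no test. All of that stands, and it sets the severity. It does not repair the rule: Appendix 3 exists for dates that a query could not resolve, and correcting an absurd value after unblinding would be a post hoc change to a comparative table.

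A second reply is that a stop after Final Follow-up can be genuine, because Protocol 21.2 has investigators follow events until they subside or stabilise. That is right. A reader might infer that any stop after Final Follow-up is an error; the documents do not support this, and the limit must allow for later contact.

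Three other stronger readings fail.

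- A reader might infer that an episode with both days missing in the first-dose month always receives the whole treatment course as its duration. That needs the last dose in the same month. With first dose 25 June, last dose 5 July and both dates recorded as 'June', the rules give 25 to 30 June: 6 days of an 11-day course.
- A reader might call the switch between last-dose date and month end a defect that requires one rule for a missing day. Anchoring a same-month stop to the last dose is a defensible choice, and subjects with different last-dose dates do not carry the same information.
- A reader might put the New Year exposure at 30/365 to 37/365, or 8% to 10%. That counts subjects whose last dose falls after New Year, for whom a stop in that year goes to the last-dose date.

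**Conclusion.** The rule is wrong as written, at low severity. Imputed stop dates have no upper limit: the year rule can place a stop 334 to 365 days after Final Follow-up, and the month rule placed it 31 to 38 days after in the example worked. The values enter the nausea-duration summary, where one record could take an arm's mean from 2.5 to between 6.4 and 13.0 days and would also inflate the standard deviation and maximum.

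These means rest on an assumed 2.5-day true duration, on nausea rates carried over from earlier studies, and on one affected record actually occurring. The documents do not give the number of unresolved partial dates; it should be very small. Efficacy results, treatment-emergent classification and nausea event counts are unaffected.

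**What to change.** Add to SAP Appendix 3, as a last step after the existing rules and note: an imputed adverse-event stop date may not be later than the later of the Final Follow-up date and the last documented contact, and may not be earlier than the start date. Where the recorded month or year lies wholly after that limit, use the first day consistent with what was recorded, so that site information is not overridden.

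Optionally, add a supplementary line to the SAP 11.1 nausea table giving duration for events with complete dates and the number omitted. Keep the summary of all nausea events, because dropping incomplete records could itself bias duration. The choice between last-dose date and month end can stay as it is.

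The cost is a sentence or two in the SAP and minor programming, best done before unblinding.
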